Yes

VIII.6 *List names:*

[name], MD, PhD, Professor of Anesthesiology, Department of Anesthesiology, UIHC.

VIII.7 *Will overall safety monitoring be performed by individuals or committee not associated with The University of Iowa (such as a study Data Safety Monitoring Board)?*

No

IX. Benefits

IX.1 *What are the direct benefits to the subject (do not include compensation or hypothesized results)?*

None

IX.2 *What are the potential benefits to society in terms of knowledge to be gained as a result of this project?*

Difficult and failed mask ventilation are a significant risk after induction of anesthesia. As risk factors for difficult and failed mask ventilation (such as obesity and age >55) are increasing in the population as a whole, methods for optimizing mask ventilation are becoming even more crucial. There are no oral airways currently available which actively displace oropharyngeal obstructions, as the AOA does. The potential benefits of the AOA relate to better caring for patients who are at risk for difficult mask ventilation. The AOA also has the additional functionality of facilitating flexible scope (fiberoptic) intubation, though that functionality is not being tested as part of this protocol.

X. Privacy & Confidentiality

X.1

What are you doing to protect the [privacy](#) interests of the subjects?

All communication with subjects will be done in a private room with the doors closed. Information that can not be obtained from the medical record will be asked in person. There will be no pictures or videos taken of patients or patient identifiers. Only information related to the study will be collected and only the minimum amount of personal/private information needed to answer the study questions will be collected.

X.2

Are you collecting the Social Security Number of any subjects for any purpose?

No

X.4

How will information/data be collected and stored for this study (check all that apply):

- Paper/hard copy records (hard copy surveys, questionnaires, case report forms, pictures, etc.) - Paper/hard copy records (hard copy surveys, questionnaires, case report forms, pictures, etc.) - Case report forms will be kept separate from informed consents in 3 hole punched binder. They will be kept in locked file cabinets in a locked office of one of the research assistants. The CRF will have a study ID number for identification. One data list will be kept of the subjects name and ID number for identification purposed on a password protected document within a password protected file. The intraoperative video will contain no images of the patient or patient identifiers, just the anesthesia monitor and the device randomized to be placed first. The video will be uploaded to a password-protected server (backed up and overseen by UI department of anesthesia ITS) to which only study personnel will have access. After upload, the original video will be deleted.
- Electronic records (computer files, electronic databases, etc.) - Electronic records (computer files, electronic databases, etc.) - One data list will be kept of the subjects name and ID number for identification purposed on a password protected document within a password protected file.
 - Name - [name]
 - Title - Information Technology Security Officer
 - University Job Classification - System Administrator and Systems Programmer II

X.5

Do the confidentiality protections indicated above allow only members of the research team to access the data/specimens?

Yes

X.7

Does your study meet the NIH criteria for a [Certificate of Confidentiality](#) or will you be applying for Certificate of Confidentiality?

No

XI. Data Analysis

XI.1

Describe the analysis methods you will use, including, if applicable, the variables you will analyze

We will use non-inferiority testing for the analysis of the primary outcome variable in this study. We will assume that the Articulated Oral Airway is non-inferior to the Guedel oral airway if the difference in expiratory tidal volume measurements between the two devices is less than 1ml/kg.

XI.2

Provide the rationale or power analysis to support the number of subjects proposed to complete this study.

We will assume that the AOA is non-inferior to the GDA if the difference in expiratory tidal volume measurements between the two devices is less than 1ml/kg. With a sample size of 55 patients, a paired t-test of equivalence of means with a 0.050 one-sided significance level will have 90% power to reject the null hypothesis that expiratory tidal volumes with a GDA and AOA are not equivalent (> 1ml/kg difference in expiratory tidal volumes) (SD of difference is 2.5ml/kg). To allow for 3 protocol failures, we will recruit a total of 58 patients. Note that, if the non-inferiority is satisfied, we will also explore the superiority of the AOA to the GDA. With this number of patients, the paired t-test will have >95% power to test the hypothesis that the expiratory tidal volumes measured with the AOA are 1.5ml/kg greater than with the GDA (SD of difference: 2.5ml/kg).

XII. Future Research

XII.1

Do you wish to keep any information about subjects involved with this research project so that members of the current research team may contact them in the future for your own research projects?

No

XII.2

Do you wish to keep any information about subjects involved with this research project so that other researchers may contact them for future research?

No

XII.4

Does this project involve storing any data, tissues or specimens for future research?

No

New Project Form Attachments

Attachment Name	Category	Ver	Size	Attached
Articulated Oral Airway study_Informed_consent.rtf	Informed Consent	5	181 E k	06/28/17
Articulated Oral Airway study_Record of consent.rtf	Record of Consent	1	53 k E	04/19/17
[name] GAP 2017 Aluminum Mold Upgrade Request.pdf	Funding Source Grant	1	99 k E	04/18/17
 GAP Funding Proposal (part 2, aluminum molds and biocompatible AOAs)				
[name] GAP-award-letter-forms_3x_FY16 2-1-16.docx	Funding Source Grant	1	287 E k	04/18/17
 GAP Funding Award Letter (Part 1)				
[name] GAP-award-letter-forms_3x_FY17.docx	Funding Source Grant	1	294 E k	04/18/17
 GAP Funding Award Letter (Part 2, aluminum molds a bio-compatible AOAs)				
GAP Funding Proposal (d) Articulating Oral Airway Functional Prototyping [name] MD JK.pdf	Funding Source Grant	1	246 E k	04/18/17

GAP funding proposal (part 1)	CFR - Code of Federal Regulations Title 21.pdf	Device Documentation	1	266	E k	04/18/17
The Articulated Oral Airway had been determined by the FDA to meet exclusion criteria 2 (highlighted) and thus allowed for use in this study.	FDA_Airway_Oropharyngeal_Anesthesiology_Class_1_Classification.pdf	Device Documentation	1	105	E k	05/16/17
From the FDA website: https://www.accessdata.fda.gov/scripts/cdrh/cfdocs/cfpdc/classification.cfm?start_search=1&DeviceName=&ProductCode=&ThirdParty=&DeviceClass=1&SUBMISSION_TYPE_ID=4&GMPExempt=N&Panel=&RegulationNumber=868.5110&PAGENUM=10&SortColumn=DeviceName						
AOA Blinded Video Review Data Collection Form.xlsx		Screening: Screening Log	1	21	k E	04/27/17
AOA Study Attending Data Collection Log.xlsx		Screening: Screening Log	1	18	k E	04/27/17
AOA Study: Attending anesthesiologist data collection log						
AOA Study Research Assistant Checklist and Data Collection Log.xlsx		Screening: Screening Log	1	17	k E	04/27/17
[name] AOA Current Enrollment Log.xlsx		Screening: Screening Log	1	12	k E	04/27/17
[name] AOA Declined Log.xlsx		Screening: Screening Log	1	11	k E	04/27/17
AOA Study Attending Data Collection Form.docx		Miscellaneous	1	33	k E	04/26/17
AOA Study: Attending Data Collection Form						
AOA Study Blinded Video Review Data Collection Form 4.26.17.docx		Miscellaneous	1	320	E k	04/26/17
AOA Study: Blinded Video Review Data Collection Form						
AOA Study Checklist, Data Collection Form 4.26.17.docx		Miscellaneous	1	46	k E	04/26/17
AOA Study: Research Assistant Checklist and Data Collection Form						
AOA Study Protocol, 4_26_17.docx		Miscellaneous	1	28	k E	04/26/17
AOA Study Protocol (full)						
AOA Study Roles - Attending Anesthesiologist.docx		Miscellaneous	1	18	k E	04/26/17
Study Roles: Attending Anesthesiologist						
AOA Study Roles - CRNA.docx		Miscellaneous	1	159	E k	04/26/17
Study Roles: Certified Registered Nurse Anesthetist						
AOA Study Roles - Research Assistant.docx		Miscellaneous	1	19	k E	04/26/17

 Study roles: Research Assistant					
AOA.jpg	Miscellaneo us	1	102 k	E	06/28/17
 AOA (investigational device)					
[name] patent for airway device.pdf	Miscellaneo us	1	303 k	E	06/26/17
Email_Verification of no conflict of interest regarding clinical study of the Articulated Oral Airway.msg.pdf	Miscellaneo us	1	72 k	E	04/26/17

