Title: The Articulated Oral Airway as an Aid to Mask Ventilation, a Prospective Interventional, Non-Inferiority Study

NCT# 03144089

[name]

May 16, 2021

AOA Testing

PI: [name]
IRB ID #: 201704829

Form Content

I. Project Introduction

I.1 *Project to be reviewed by:*
IRB-01

I.2 *Project Title:*
The Articulated Oral Airway as an Aid to Mask Ventilation, a Prospective Interventional, Non-Inferiority Study

I.3 *Short Title (optional):*
AOA Testing

I.4 *Provide a short summary of the purpose and procedures of the study proposed in this IRB application.*

- ***DO NOT include information on studies not proposed in this application.***
- ***Use LAY terminology only. This must be easily understandable by IRB community members and nonscientists.***
- ***DO NOT cut and paste technical abstracts from funding applications that may not be understood by a general audience.***

The Articulated Oral Airway (AOA) is a new, FDA Class 1 (exempt from pre-market notification), device which assists in airway management, specifically mask ventilation. The AOA is currently being developed by the University of Iowa Research Foundation (UIRF Case# 2014-018) in conjunction with the Primary Investigator. The device has gone through two phases of human analog (mannequin) testing, with another round scheduled. After the third round of mannequin testing, bio-compatible (safe for oral use) prototypes will be made in a ISO 9001:2008 Certified molding facility. We plan to test these bio-compatible prototypes in healthy human volunteers to assess real-world function.

Patients who are predicted to be difficult to breath for after going to sleep (and meet inclusion criteria/do not meet exclusion criteria) will be offered enrollment in the study. Those that enroll will have their airway maintained with two different designs of oral airway (soft plastic oral stents) to see if one works as well as the other. To determine this we will be looking at how big a breath is achieved with a set pressure via the ventilator through each device. We will also be examining the devices after removal, and seeing the patients in the recovery room, to evaluate for any difference in oral or throat trauma. As patients will be anesthetized and breathed for regardless of their enrollment status, their day will be no different aside from speaking with a study team member prior to surgery and again in the recovery room.

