I.5 *Specify your research question(s), study aims or hypotheses (do not indicate "see protocol")*

- 1) Does the AOA facilitate mask ventilation (as measured by inspiratory and expiratory tidal volumes and end-tidal CO₂ waveforms) as well as a Guedel oral airway in patients with risk factors for difficult mask ventilation
- 2) Is the AOA non-traumatic as anticipated to the human airway

I.6 *Background and significance and/or Preliminary studies related to this project. (do not indicate "see protocol")*

Brief explanation: The Articulated Oral Airway (AOA) is a novel device in the field of Airway Management which actively facilitates both mask ventilation (breathing for an anesthetized patient without a breathing tube) and fiberoptic intubation (placement of a breathing tube using a flexible

camera). No device currently on the market has this dual functionality. In conjunction with the University of Iowa Research Foundation (UIRF Case# 2014-018) the AOA received US Patent 8,794,230 B2 in August of 2014.

Detailed explanation: A primary goal of all anesthetics is the establishment of a patent airway. The most commonly performed airway management technique is mask ventilation; using a mask over a patient's nose and mouth to breath for them. This technique is made significantly more difficult by certain anatomical features, the most common of which is a large tongue related to obesity. The AOA not only creates a conduit for delivering oxygen and anesthetic agents, but also actively displaces the tongue to optimize the space available for ventilation.

In addition, the AOA can act as a conduit for flexible fiberoptic intubation – a technique of utilizing a flexible guide to navigate airway anatomy and allow placement of a breathing tube ("endotracheal tube," or ETT) with minimal manipulation of a patient's neck and airway. A significant disadvantage of fiberoptic technique is that, for an image to be seen, an "airspace" (a space void of visual obstruction) must be created. If the tip of the fiberoptic scope is touching the patient's airway or any foreign objects in the patient's airway, the result would be analogous to leaving the lens cap on a camera and the necessary anatomy would not be seen.

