VI.2 *What is the age of the youngest adult subject?*
18.0

VI.3 *What is the age of the oldest adult subject?*
99.0

VI.4 *What is the percentage of adult male subjects?*
70

VI.5 *What is the percentage of adult female subjects?*
30

VI.6 *How many minor subjects do you expect to consent or enroll for this project?*
0

VI.13 *Describe EACH of your subject populations*

- *Include description of any control group(s)*
- *Specify the Inclusion/Exclusion criteria for EACH group*

Control group(s): None, each patient will be their own control

Inclusion Criteria: Patients undergoing non-emergent surgery who have two or more of the following risk factors for difficult mask ventilation:

- i. Age > 55 years
- ii. BMI > 30kg/m²
- iii. Beard
- iv. Lack of teeth
- v. History of snoring

Exclusion Criteria:

- a. Documented history of impossible MV
- b. Planned omission of mask ventilation [i.e. Rapid Sequence Intubation ("RSI," a modified induction routine which omits mask ventilation and is used when risk of aspiration is high)]
- c. Planned omission of long-acting paralytics
- d. Need for awake airway management
- e. Need for emergent airway protection
- f. Presence of oropharyngeal anatomic abnormalities
- g. Distance from the maxillary incisors to the angle of the mandible <11cm
- h. <18 years of age
- i. Known pregnant state
- j. Current incarceration
- k. Refusal to be involved in the study

With the above inclusion (i.e. presence of beard) and exclusion (maxillary incisor to angle of mandible distance <11cm) criteria, we anticipate that roughly 70% of eligible patients to be male, as women are less likely to have a beard or high maxillary incisor to angle of mandible distance.

VI.14 *Provide an estimate of the total number of subjects that would be eligible for inclusion in each of your study populations (include your control population if applicable)*
Review of EPIC UIHC Main Operating Room (MOR) and Ambulatory Surgery Center (ASC) schedules show that a typical day consists of 90-110 surgeries. Of these patients, roughly 4-8 patients would be expected to meet inclusion (and not meet exclusion) criteria per day.

VI.15 *Describe how you will have access to each of your study populations in sufficient number to meet your recruitment goals.*
 As per above, there are historically 4-8 patients per day who would qualify for the study. With the goal of consenting 1-2 per day, we should be able to enroll 58 patients in 50-60 OR days, or 10-12 weeks.

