Age, Body Mass Index (BMI), presence or absence of dentition, history of snoring or sleep apnea, type of surgery scheduled, and airway management history.

VII.D.3 *Describe why you could not practicably recruit subjects without access to and use of the information described above*
It would be impractical to interview every operating room patient (90-110 per day). Pre-screening will allow for us to approach <10 patients per day instead of >90.

VII.D.4 *Describe why you could not practicably obtain authorization from potential subjects to review their patient or clinic records for recruitment purposes.*
It would be impractical to call and obtain authorization for chart review of every operating room patient (90-110 per day).

VII.D.5 *Describe plans to protect the identifiers from improper use or disclosure*
If inclusion criteria are met via chart review, only the patients Medical Record Number (MRN) and scheduled time of surgery will be recorded. No additional information (medical or otherwise) will be recorded along with the MR. Recorded information will be

	only be seen by study members and will be confidentially destroyed after patient recruitment.				
VII.D.6	
Describe plans to destroy identifiers at the earliest opportunity consistent with conduct of the research
 
Once a patient is consented for the study, they will be assigned a study patient number which will not be associated with the patient's medical record or MRN. If a patient declines participation in the study, the patient information will be immediately disposed of (either shredded or placed in a locked hospital provided confidential information disposal bin).
				
VII.D.7	
Does the research team agree that the requested information will not be reused or disclosed to any other person or entity, except as required by law, for authorized oversight of the study, or for other research for which the use or disclosure of the requested information would be permitted by the HIPAA Privacy Rule
 
Yes
				
VII.D.8	
Will a member of the research team discuss the study with the subject in person prior to the subject agreeing to participate?
 
Yes
				
VII.D.9	
Describe the physical location where the consent process will take place:
 
The consent process will take place in the Day of Surgery Area (DOSA, UIHC Main OR), Pre-operative waiting area (UIHC Ambulatory Surgery Center), or UIHC inpatient rooms.
				

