- AOA: In the “closed” conformation, insert with concavity facing upward then turn 180 degrees as advancing the proximal bevel to the level of the teeth. Once at the level of the teeth, bring proximal ends together to lock in the fully ‘open’ conformation

12) The CRNA will turn back to the patient and secure the anesthesia mask utilizing “2-handed jaw-thrust” technique.

13) The ventilator is turned on and the following data is recorded, via video of the anesthetic monitor, for breaths # 6-10:

-Inspiratory tidal volumes

-Expiratory tidal volumes

-EtCO₂ waveform

Note (a): If EtCO₂ is not achieved after 5 breaths with first device, proceed immediately to step #14

Note (b): No video or images will be taken of the patient or patient identifiers, just the anesthesia monitor and the device randomized to be placed first

14) The CRNA will then turn away from the patient and the RN research assistant or study medical student will remove the oral airway, noting the presence of any blood on the device (first device only)

15) Steps 10-13 will be repeated for the device randomized to be placed second, then the anesthetic will proceed at the discretion of the providers

Note: If EtCO₂ is not achieved after 5 breaths with the second device, the protocol is ended and the ASA Difficult Airway Algorithm is followed

D. Post-operative:

15-45 minutes after "Anesthesia Stop" time, the research assistant or study medical student will:

- Perform an oropharyngeal exam for signs of trauma

- Ask the patient to grade their degree of “sore throat” (subjectively, from 0-10)

E. Data Review:

-The video taken during step 13 above will be uploaded to a password-protected server to which only study personnel will have access. The video will contain no images of the patient or patient identifiers, just the anesthesia monitor and the device randomized to be placed first

-The blinded primary investigator ([name]) will transcribe clinical data (expiratory and inspiratory tidal volumes and EtCO₂ waveforms) from the above video

VII.E.7

Will you attempt to recontact subjects who are lost to follow-up?

No - followup is not required in this study

VII.E.9

Will subjects be provided any compensation for participating in this study?

No

VIII. Risks

VIII.1

What are the risks to subjects including

- emotional or psychological

- financial

- legal or social

- physical?

- Emotional or psychological: None foreseen

- Financial: None foreseen

- Legal or social: None foreseen

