- Physical: Potential for risks associated with routine airway management with an oral airway (difficult or failed airway management/oropharyngeal trauma). Potential for risks associated with placement of two oral airways instead of just one or none.

VIII.2

What have you done to minimize the risks?

- *If applicable to this study ALSO include:*
 - *How you (members of your research team at Iowa) will monitor the safety of individual subjects.*
 - *Include a description of the availability of medical or psychological resources that subjects might require as a consequence of participating in this research and how referral will occur if necessary (e.g. availability of emergency medical care, psychological counseling, etc.)*

Pre-procedure: The Articulated Oral Airway is made of bio-compatible material in a ISO 9001:2008 Certified molding facility. The AOA has been tested in manakin models, including pressure testing by members of the UIowa Biomedical Engineering program.

Intraoperative: Per protocol, if difficulty in airway management is encountered, the study is abandoned and emergency airway management protocols (ASA Difficult Airway Algorithm) followed.

Post-operative: An interim safety review will be performed after 20 patients have been enrolled. If there is any significant increase in either trauma or difficult in mask ventilation noted, the study will be stopped.

VIII.3 *Does this study have a plan to have an individual or committee review combined data from all subjects on a periodic basis (such as summary or aggregate safety and/or efficacy data)?*

Yes

VIII.4 *Describe the plan to review combined data from all subjects, such as summary or aggregate safety and/or efficacy data. Include the following:*

- *Describe what data will be summarized and reviewed*
- *Describe how frequently data will be reviewed.*

After the first 20 patients (and any time earlier if concerns are raised by the research team/clinical staff caring for the patients), a unbiased faculty anesthesiologist ([name], as per below) will review intraoperative tidal volumes (marker for adequate ventilation), incidence of blood on first-placed device, and post-anesthesia care unit (PACU) data on post-operative pharyngeal trauma.

VIII.5 *Will overall safety monitoring be performed by individual(s)/committee at The University of Iowa. (NOTE: If this study involves more than minimal risk, in most cases these should be individuals who are not members of the study research team.)?*

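### Surgery in the mouth or throat is not excluded, so the recovery-room exam and sore-throat score can count surgical injury as airway trauma

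*Combined protocol and SAP*

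**What the plan says.** **Who is eligible.** VI.13 takes "Patients undergoing non-emergent surgery who have two or more of the following risk factors for difficult mask ventilation". The five factors are age, BMI, beard, lack of teeth and snoring. Exclusions a to k deal with airway history, airway plan, urgency, anatomy, age, pregnancy, incarceration and refusal. None names a surgical site. The closest is f, "Presence of oropharyngeal anatomic abnormalities".

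**What is known at screening.** The chart items listed in VII.D.2 include "history of snoring or sleep apnea, type of surgery scheduled, and airway management history". No criterion in VI.13 uses the surgery type to restrict site.

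**What is measured afterwards.** VII.E.6, part D, has a research assistant or medical student "Perform an oropharyngeal exam for signs of trauma" and take a 0-10 sore-throat score, 15-45 minutes after anesthesia stops.

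**What it is for.** The second aim in I.5 asks: "Is the AOA non-traumatic as anticipated to the human airway". The lay summary in I.4 describes "seeing the patients in the recovery room, to evaluate for any difference in oral or throat trauma". Under VIII.4 the 20-patient reviewer receives tidal volumes, blood on the first-placed device, and recovery-room data on pharyngeal trauma. VIII.2 adds: "If there is any significant increase in either trauma or difficult in mask ventilation noted, the study will be stopped".

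**The concern.** The exam and the score come after the operation. In a patient whose operation was on the palate, tonsils, gums or larynx, a fresh lesion or a sore throat is expected whichever airway device was used. The plan describes no baseline trauma exam, no rule for attributing a finding to the device or to the surgery, and no separation of results by surgical site. Two of the inclusion factors, snoring and lack of teeth, are plausible in patients booked for such surgery, and exclusion f does not cover a normal mouth that is about to be operated on.

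At stake are the pooled rate of recovery-room trauma reported for Aim 2 and one of the three kinds of data that the safety reviewer sees at 20 patients.

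**Working it through.** **The plan's own figure.** The documents give no figure for trauma or sore throat. The only power figure (XI.2) concerns expiratory tidal volume: 55 patients, margin 1 ml/kg, SD of the difference 2.5 ml/kg, one-sided 0.05. The noncentral t calculation for a one-sided paired test gives 0.9005 against the stated 90%, so it reproduces. It does not depend on this point, because tidal volumes are recorded before surgery.

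**Which measures are exposed.**

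| Measure | When recorded | Can reflect surgery? | Named for the 20-patient review (VIII.4)? |
|---|---|---|---|
| Tidal volumes | Induction, before surgery | No | Yes |
| Blood on first-placed device | At its removal, before surgery | No | Yes |
| Oropharyngeal exam | After surgery | Yes | Yes, as pharyngeal trauma |
| Sore-throat score | After surgery | Yes | Not named |

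**How often it could arise.** Let f be the share of enrolled patients having mouth or throat surgery. The documents do not give f, so the range 2-15% is an assumption. With 20 patients at the review and 58 recruited:

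- chance of at least one in 20 = 1 − (1 − f)^20
- expected number = 20f at the review and 58f overall

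| f | At least one in 20 | Expected in 20 | Expected in 58 |
|---|---|---|---|
| 2% | 1 − 0.98^20 = 33% | 0.4 | 1.2 |
| 5% | 1 − 0.95^20 = 64% | 1.0 | 2.9 |
| 10% | 1 − 0.90^20 = 88% | 2.0 | 5.8 |
| 15% | 1 − 0.85^20 = 96% | 3.0 | 8.7 |

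**What it could do to the pooled rate.** Suppose the true airway-trauma rate is p and, as a worst case, every such patient shows surgical injury that is counted. The apparent rate is p(1 − f) + f. With p = 5% (also an assumption):

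- f = 2%: 0.05 × 0.98 + 0.02 = 6.9%
- f = 5%: 0.05 × 0.95 + 0.05 = 9.8%
- f = 10%: 0.05 × 0.90 + 0.10 = 14.5%
- f = 15%: 0.05 × 0.85 + 0.15 = 19.3%

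**Precision.** If no patient of 58 had airway trauma, the exact (Clopper-Pearson) one-sided 95% upper limit would be 1 − 0.05^(1/58) = 5.0%. One miscounted surgical case moves it to 7.9%, and three move it to 12.8%. The plan specifies no such limit; these values only show how sensitive a small count is.

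**The case against.** The strongest reply is that little of the trial is touched and that the change gains little. Much of this stands.

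- **The primary outcome is safe.** Tidal volumes precede surgery, and the sample size rests on them alone.
- **The device-specific trauma measure is safe.** Blood on the first-placed device is noted at removal. VII.E.2 gives it as the first reason for randomizing the order, and the reviewer also receives it. A reader might infer that Aim 2 and the safety stop rest on recovery-room data alone; they do not.
- **Recovery-room findings are non-specific anyway.** Every patient has had both devices, possibly a nasopharyngeal airway, and then whatever airway management the providers chose. Removing surgical injury cleans a pooled rate that still cannot be assigned to the AOA. For a comparison between order groups, randomization makes surgical injury noise and not systematic bias. It does not, however, take that injury out of the pooled rate.
- **Case mix is unknown.** Exclusion f removes some of these patients, and the documents give no basis for any value of f.
- **Other forms may help.** The attachment list names data collection forms and a full protocol that could record surgical site. VII.B.11 says there is no separate protocol, so this is only a caution.

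Two stronger readings are tempting. One is that the sore-throat score feeds the stop: VIII.4 does not name it. The other is that a false stop is likely: VIII.2 requires a significant increase, a faculty anesthesiologist reviews the data, and nothing shows that this reviewer would take an expected operative wound for device trauma. With no threshold or comparator stated, a false stop is possible, but it is not demonstrated.

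**Conclusion.** The concern holds in a limited form. As written, the plan admits patients whose operation can itself produce the findings that the recovery-room exam and sore-throat score look for, and it gives no way to set those findings aside. This can inflate the pooled recovery-room trauma findings for Aim 2 and, through the exam, the pharyngeal-trauma data in the 20-patient review.

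The size depends on an unknown share. At an assumed 2-15%, the chance that at least one such patient is among the first 20 runs from 33% to 96%. That is the chance of enrolling one, not of miscounting one or of stopping the study. The inflated rates shown above also assume that every such patient is counted as trauma. The primary comparison, its power and the first-device blood measure are unaffected. The change is worth making because it is cheap, but it does not make the recovery-room findings specific to the AOA.

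**What to change.** Choose one and write it into the plan.

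1. **Exclude.** Add to VI.13 an exclusion for planned surgery or instrumentation of the mouth, pharynx or larynx, beyond routine airway management. Apply it at schedule review from the item "type of surgery scheduled", which is already read. *Cost:* a slightly smaller pool. VI.14 expects 4-8 eligible patients a day against a goal of 1-2 (VI.15). Losing 15% of the lower figure leaves 4 × 0.85 = 3.4 a day, still above the goal.
2. **Keep, but restrict the summaries.** Enroll these patients for tidal volume and first-device blood. Record the surgical site, and leave them out of the recovery-room trauma and sore-throat summaries and out of the recovery-room part of the 20-patient review. *Cost:* at the assumed 2-15%, about 1 to 9 fewer of 58 patients in those summaries (58 × 0.02 = 1.2; 58 × 0.15 = 8.7).

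Neither option changes the primary analysis or the sample size.
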